Nudging Flu Vaccination in Patients at Moderately High Risk for Flu and Flu-related Complications

Study Protocol with SAP

NCT05509283

10/25/2022

Study Protocol

Scientific Background

Almost everyone ages 6 months or older can benefit from the influenza vaccine, which can reduce illnesses, missed work, hospitalizations, and death by reducing the likelihood of contracting influenza. Flu shots are particularly important for patients at high risk of experiencing severe outcomes.

In the 2020–21 and 2021–22 flu seasons, the study team sent messages to Geisinger patients in the top 10% of risk for flu and complications according to an artificial intelligence algorithm. Messages that disclosed patients' risk status significantly increased flu vaccination rates. Additionally, messages that included risk information were most effective in patients at relatively lower risk (those in the top 4–10%) compared with those at the highest risk (top 3%).

Objectives

The present work will test the effectiveness of high-risk messages in patients who are in the top 11–20% of risk, at high risk but lower than previous studies. These communications will inform patients they are at high risk with either (a) no additional explanation, (b) an explanation that this determination comes from an analysis of their medical records, or (c) the additional explanation that an AI or ML algorithm made this determination.

Design

This study is a randomized controlled trial with 5 study arms. Patients were randomized to receive (or not receive) one of several messages about flu shots.

Methods

The sample includes 40,671 patients. Patients were randomized into the following study arms:

1. Passive Control - Patients in the passive control arm did not receive additional pro-vaccination interventions beyond the health system's normal efforts.
2. Active Control - Patients in the active control arm received messages reminding them to get a flu shot without advising them of their risk status.
3. High Risk Only - Patients in this treatment arm received messages telling them they were identified to be at high risk for flu complications, without specifying how or why the health system believes this to be the case.
4. High Risk with Explanation Based on Medical Records - Patients in this treatment arm received messages telling them they were identified to be at high risk for flu complications via review of their medical records.
5. High Risk with Explanation Based on Algorithm - Patients in this treatment arm received messages telling them they were identified to be at high risk for flu complications via analysis of their medical records by a computer algorithm.

Power Analysis

The sample size above allows 80% power to detect an increase in flu vaccination rates from 35% to 37.1% with two-tailed alpha = .05 for any comparison between study arms.

Message Modalities

Patients randomized to arms 2-5 were sent messages in up to 3 modalities, depending on eligibility: 1. a letter, 2. a MyGeisinger (MyChart patient portal) message, and 3. a short message service (SMS) message.

Project Status

All intervention messages have been sent.

Letters for the Active Control and High Risk with Explanation Based on Algorithm study arms were sent on 9/13/22. Due to a miscommunication with the mail room, letters for the High Risk Only and High Risk Based on Medical Records arms were delayed by one day (send date of 9/14/22).

Patient portal messages were sent on 9/27/22 for all study arms.

Patients eligible for SMS were randomized to be sent a message on 10/12/22 or 10/13/22. Randomization was stratified by study arm.

Data collection is ongoing within the health system, and the study team has not yet obtained or analyzed any outcome data from the study.

Change in Primary Outcome Time Frame

Our originally preregistered primary outcome time frame was within 2 weeks of the final message send date. However, due to the mistimed letters mentioned in the Project Status section, we changed the primary outcome time frame to within 6 weeks of the patient's study start date, so all patients can be monitored for the same length of time.

The study start date corresponds to the letter send date for the patient's study arm:

- 9/13/22: Active Control and High Risk with Explanation Based on Algorithm
- 9/14/22: High Risk Only and High Risk Based on Medical Records

Because patients in the Passive Control study arm were not sent a letter, they will be randomized to a study start date of 9/13/22 or 9/14/22.

Analysis Exclusion Criteria

Patients vaccinated before to their study start date. We will remove patients from analysis who received a flu shot prior to their study start date (9/13/22 or 9/14/22, depending on their study arm), because they could not have been influenced by our nudge messages to get a flu shot.

Patients deceased prior to their study start date. Twice during the study, we received updated lists of patients who were deceased. Some had died prior to the study beginning but

medical records had not yet been updated to reflect the date of death. These patients will be removed from all analyses.

Statistical Analysis Plan

Planned Analyses

Primary Outcome: Received a flu vaccination within 6 weeks of the patient's study start date [
Time Frame: Within 6 weeks of the patient's study start date]

Question 1: Does informing patients that they are at high risk for flu and flu-related complications increase the likelihood that they will get vaccinated?

Analysis 1a (Confirmatory): We will test the hypothesis that patients who were sent messages with information about their risk status (patients randomized to message arms 3, 4, or 5) will exhibit improved flu vaccination rates compared with patients in the Active Control arm who were sent messages without risk information (arm 2).

Analysis 1b (Confirmatory): We will test the hypothesis that patients who were sent messages with information about their risk status (those in arms 3, 4, or 5) will exhibit improved flu vaccination rates compared with patients assigned to the Passive Control arm (arm 1).

For analyses 1a and 1b, we will run OLS regressions. For both regressions, we will include a binary predictor variable coding separately for baseline (arm 2 for analysis 1a and arm 1 for analysis 1b), and message (all patients in arms 3–5).

Question 2: Do messages encouraging flu shots increase flu vaccination rates?

Analysis 2 (Confirmatory): We hypothesize that patients who were sent Active Control messages encouraging them to get a flu shot with no information about their risk status (arm 2) will be more likely to get a flu shot than those in the Passive Control arm (arm 1). To assess this hypothesis, we will employ OLS regression with a categorical predictor variable coding for arm.

Question 3: Among messages that mention patients' risk statuses, is it most effective to a) give patients no information about how their risk status was determined (arm 3), b) tell patients their high-risk designation was based on a review of their medical records (arm 4), or c) tell patients their high-risk designation was based on a computer algorithm review of their records (arm 5)?

Analysis 3 (Exploratory): We will evaluate this question using an OLS regression model, with a categorical predictor variable coding for arm (arm 3, arm 4, arm 5). We will run post-hoc tests using Tukey's HSD to test for significant pairwise differences between the arms.

Sensitivity Analyses and Robustness Checks

Recent work suggests that OLS regressions are appropriate in randomized experiments with binary outcome variables such as ours (Gomilla, 2021). However, as a robustness check, we will also run the regressions described above as logistic regressions instead of OLS regressions. We may run additional sensitivity analyses or robustness checks.

Other Pre-specified Outcomes

Other Pre-specified Outcomes listed below include flu outcomes (diagnosis, complications) and COVID-19 vaccination. If there are any differences in these outcomes as a function of study arm, the mechanism would almost certainly be increased flu vaccination. Therefore, we will only run analyses on Other Pre-specified Outcomes for analyses above where there is a significant difference in flu vaccination.

1. High confidence flu diagnosis

Patient received a flu diagnosis via a positive polymerase chain reaction (PCR)/antigen/molecular test (yes/no) during the 2022-23 flu season (from the patient's study start date through April 30, 2023).

[Time Frame: Up to 8 months]

2. "Likely flu" diagnosis

Received a "high confidence flu" diagnosis (with positive PCR/antigen/molecular test) and/or "likely flu" diagnosis (as assessed via International Classification of Disease [ICD] codes or Tamiflu administration or positive PCR/antigen/molecular test) (yes/no) during the 2022-23 flu season (from the patient's study start date through April 30, 2023).

Note that "likely flu" is a superset of the "high confidence flu" diagnoses.

[Time Frame: Up to 8 months]

3. Flu complications

Diagnosed with flu-related complications (yes/no) from the patient's study start date through July 31, 2023.

[Time Frame: Up to 11 months]

4. ER visits

Number of ER visits from the patient's study start date through July 31, 2023.

[Time Frame: Up to 11 months]

5. Hospitalizations

Number of hospitalizations from the patient's study start date through July 31, 2023.

[Time Frame: Up to 11 months]

6. COVID-19 vaccination rates

Received at least one COVID-19 vaccination (yes/no) during the 2022-23 flu season (from the patient's study start date through April 30, 2023).

[Time Frame: Up to 8 months]

Additional Exploratory Analyses

1. Age and gender

While older patients tend to be aware of their increased vulnerability, younger patients may be more surprised to learn of their high-risk status. Additionally, our previous work suggests that males and females are differently likely to get vaccinated as a function of age, with younger females *more* likely to get vaccinated than males, and older females *less* likely to get vaccinated than older males.

To test the relation between flu shots, age and gender, we will run an OLS regression including binned age (18–24, 35–44, 45–54, 65+), gender, and their interaction.

Finally, we will test for an interaction between age, gender, and study arm, as people of different ages and genders may be differentially receptive to different message versions.

2. Timing of shot

We will examine outcomes over time and run regression models to test whether intervention messages influenced the timing (time elapsed since the beginning of the intervention, September 13, 2022) of flu shots.

3. Risk level

We will explore heterogeneity in flu vaccination rates within the top 11–20% of risk, and test whether effects of study arm vary as a function of risk level.

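### The 80% power claimed for every between-arm comparison does not hold for the exploratory Tukey comparisons of arms 3 to 5, where a named pair has about 67%

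*Combined protocol and SAP*

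**What the plan says.** The Methods section gives the sample: "The sample includes 40,671 patients", randomised to five arms. The allocation ratio is not stated. The Power Analysis section says that this sample gives 80% power to detect a rise "from 35% to 37.1% with two-tailed alpha = .05 for any comparison between study arms". It makes no exception and does not mention multiplicity.

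The SAP then plans four tests of one single arm against another on the primary outcome:

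- **Analysis 2 (confirmatory), arm 2 vs arm 1.** "To assess this hypothesis, we will employ OLS regression with a categorical predictor variable coding for arm". No adjustment is described.
- **Analysis 3 (exploratory), arms 3 vs 4, 3 vs 5 and 4 vs 5.** The model comes first ("Analysis 3 (Exploratory): We will evaluate this question using an OLS regression model"), followed by Tukey's "HSD to test for significant pairwise differences between the arms". The family-wise level is not stated.

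Analyses 1a and 1b are of a different kind: they pool arms 3 to 5 against one control arm.

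The Analysis Exclusion Criteria section adds: "We will remove patients from analysis who received a flu shot prior to their study start date". It says of patients who had died before their start date: "These patients will be removed from all analyses". The expected number excluded is not given.

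**The concern.** The power sentence covers every between-arm comparison at a two-tailed alpha of .05, yet three of the four planned single-arm contrasts will not be tested at that level. Tukey's procedure over three arms needs a larger difference for significance, so power at 2.1 points must be below the stated figure for those pairs.

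The stake is the reading of Question 3, which asks which of the three risk messages works best. Suppose arm 4 vs arm 5 is not significant. A reader relying on the Power Analysis section would put the chance of missing a true 2.1-point difference at 20%. Under the planned test it is about 33%.

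A smaller point is that the power figure uses all randomised patients, although the plan removes some of them before analysis.

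**Working it through.** **Inputs**

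- Total 40,671 and five arms (Methods, Design). Equal allocation is assumed: n = 40,671/5 = 8,134.2 per arm.
- Rates 35% and 37.1%, two-tailed alpha .05 (Power Analysis).
- Tukey's HSD over three arms (Analysis 3). Family-wise .05 is assumed; it is the only alpha in the documents.

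**Step 1: reproduce the plan's figure**

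SE = √[(p₁(1−p₁) + p₂(1−p₂))/n] = √[(0.35×0.65 + 0.371×0.629)/8,134.2] = √(0.460859/8,134.2) = 0.00753, or 0.753 points.

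z = 0.021/0.00753 = 2.790.

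Power = Φ(2.790 − 1.960) = Φ(0.830) = 79.7%.

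The difference detectable with 80% power is about (1.960 + 0.842) × 0.753 = 2.11 points. So the stated 80% is right for an unadjusted comparison of two single arms. The agreement supports equal allocation and shows that the figure contains no multiplicity adjustment.

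**Step 2: the test planned for arms 3 to 5**

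The studentised range quantile for three groups and about 24,400 degrees of freedom is q = 3.3147. The critical value for a pairwise z is q/√2 = 3.3147/1.4142 = 2.344, a two-sided per-pair level of 0.0191.

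Power for a named pair = Φ(2.790 − 2.344) = Φ(0.446) = 67.2%. Simulation of the three-arm OLS analysis with pooled variance gives 67.1% to 67.4%, depending on the third arm's rate.

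Detectable difference with 80% power: about (2.344 + 0.842) × 0.753 = 2.40 points.

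Patients per arm for 80% power at 2.1 points, from (c + 0.842)² × 0.460859/0.021², where c is the critical value:

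- unadjusted (c = 1.960): about 8,202
- Tukey pair (c = 2.344): about 10,604

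**Step 3: what this means for Question 3 as a whole**

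Simulated Tukey results at 8,134 per arm:

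| True rates in the three arms | At least one significant pair | Best arm significantly above both others |
|---|---|---|
| 35 / 35 / 37.1 | 82% | 53% |
| 35 / 36.05 / 37.1 | 70% | not given (see note) |
| 35 / 37.1 / 37.1 | 82% | no single best arm |

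Note: in the middle row the best arm leads the second by only 1.05 points, so it is not a 2.1-point scenario for that column.

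**Step 4: confirmatory pooled analyses**

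For 1a and 1b, three arms (24,402.6) against one (8,134.2):

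SE = √(0.2275/8,134.2 + 0.233359/24,402.6) = 0.613 points; z = 0.021/0.00613 = 3.43; power = Φ(3.43 − 1.96), about 93%. The difference detectable with 80% power is about 1.7 points.

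**Step 5: exclusions**

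The documents give no share, so these are assumed values, with the 35% rate held fixed:

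| Assumed exclusion | n per arm | Unadjusted pair | Named Tukey pair |
|---|---|---|---|
| 0% | 8,134 | 79.7% | 67.2% |
| 1% | 8,053 | 79.3% | 66.7% |
| 5% | 7,727 | 77.6% | 64.6% |
| 10% | 7,321 | 75.4% | 61.9% |

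**The case against.** The strongest reply is that the sentence states its own condition, alpha = .05, and that under this condition the figure is correct for any two single arms, including pairs among arms 3 to 5. Read that way, it contains no miscalculation. This stands as far as it goes: the sum is right for the test it describes. It does not rescue the scope of the sentence, because the plan never tests those three pairs at an unadjusted .05.

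A second reply is that Analysis 3 is exploratory, its Tukey tests are post hoc, and nothing says that the trial was sized for them. That is true, and it limits the consequence. But the power statement was extended to every comparison, and Question 3 is one of the three numbered questions in the SAP.

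Third, the named-pair figure is the less favourable summary. An omnibus test at .05 in the three-arm model, which the plan does not explicitly name, would have about 83% power when one arm differs from two equal arms and about 70% when the middle arm lies halfway. The chance of at least one significant Tukey pair is similar. So a wholly null Analysis 3 is less likely than 67% suggests. This stands, but it does not change the power of a particular pair.

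Fourth, the result depends on the planning rate. For the same 2.1-point gap, power for a named Tukey pair is about 71% from a base of 30% and about 76% from 25%. This also stands: 67% belongs to the plan's own 35%.

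Finally, the messages have been sent, so the sample size is fixed, and a confidence interval will tell a reader more than planned power. Both are fair. They argue for a correction of wording only, which is all that is asked.

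**Conclusion.** The concern holds. The stated power is correct for Analysis 2 before exclusions and is exceeded for 1a and 1b. It is wrong as written for the three pairwise comparisons in Analysis 3: about 67% for a named pair instead of 80%, and 2.40 instead of about 2.1 points detectable with 80% power. If one message leads both others by 2.1 points, the chance that Tukey shows it significantly above both is about 53%.

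These figures rest on equal allocation, a Tukey family-wise level of .05 and the plan's 35% base rate. Exclusions would lower every figure somewhat, by an amount that the documents do not allow one to determine. This is an overbroad statement about exploratory comparisons. It is not a flaw in the design or in the confirmatory tests.

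**What to change.** In the Power Analysis section, replace the claim for all between-arm comparisons with wording such as:

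*This sample gives 80% power for 35% vs 37.1% in an unadjusted two-sided .05 test of two single arms (Analysis 2). For the exploratory Tukey comparisons of arms 3 to 5 (family-wise .05), power for a given pair at this difference is about 67%, and about 2.4 percentage points is detectable with 80% power. Figures assume 40,671/5 patients per arm, before exclusions.*

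Alternatively, give the figures for the expected analysed sample and state the assumed exclusion share. At an assumed 5%, for example, the differences detectable with 80% power are 2.16 points for Analysis 2 and 2.46 points for a Tukey pair. The family-wise level for Tukey should be stated in either case. A separate figure for 1a and 1b (about 93% power; 1.7 points detectable) is optional, since the present sentence does not overstate power for them.

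The cost is one reworded paragraph and a less favourable figure for the exploratory comparisons. No patients, tests or thresholds change. According to the Project Status section, the study team had not yet obtained outcome data, so at this version the correction could not be driven by results.

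### Analyses 1a, 1b, 2 and 3 use study arm as the only predictor; adding age, gender and risk level as covariates would give a small, cheap gain in precision.

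*Combined protocol and SAP*

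**What the plan says.** In the Statistical Analysis Plan, Analyses 1a and 1b are OLS regressions comparing pooled arms 3–5 with arm 2 and with arm 1: "we will include a binary predictor variable coding separately for baseline" and for message. For Analysis 2 (arm 2 against arm 1), "we will employ OLS regression with a categorical predictor variable coding for arm". Analysis 3 enters arms 3, 4 and 5 as one categorical predictor, followed by Tukey's HSD. Under Sensitivity Analyses and Robustness Checks, "we will also run the regressions described above as logistic regressions instead of OLS regressions". That section also leaves room for further checks but names none.

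Baseline variables appear only under Additional Exploratory Analyses. On age and gender, "our previous work suggests that males and females are differently likely to get vaccinated as a function of age", with the gender difference reversing between younger and older patients; accordingly "we will run an OLS regression including binned age (18–24, 35–44, 45–54, 65+), gender, and their interaction". On risk level, the plan will "test whether effects of study arm vary as a function of risk level".

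The Project Status section states that outcome data had been neither obtained nor analysed. The Power Analysis section claims 80% power for 35% against 37.1% between any two arms at two-sided alpha 0.05.

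**The concern.** With OLS on a randomised comparison, covariates fixed at randomisation leave the risk difference as the target and remove whatever outcome variance they explain. The trial will already hold age, gender and risk level, and the sponsor's earlier work suggests that age and gender together relate to vaccination. Leaving them out of the confirmatory models gives up that precision.

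The stake is power. Analysis 2 is a confirmatory comparison of two single arms with no cushion above its nominal 80%. Patients vaccinated or deceased before their start date will then be removed, and the sample cannot be enlarged because all messages have been sent. The pairwise contrasts of Analysis 3 have less power still, because of the Tukey adjustment. Bias and type I error are not at stake.

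**Working it through.** **Inputs.** From the protocol: 40,671 patients, five arms, 35% against 37.1%, two-sided alpha 0.05. Assumed: equal allocation (the ratio is not stated), so n = 40,671/5 = 8,134.2 per arm. Also assumed: R², the share of outcome variance explained by the covariates, between 0.5% and 5%.

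**The plan's own figure.** Power = Φ[(Δ − z·SE₀)/SE₁], with Δ = 0.021 and z = 1.96.

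- Pooled rate = (0.35 + 0.371)/2 = 0.3605
- SE₀ = √(2 × 0.3605 × 0.6395/8,134.2) = 0.007529
- SE₁ = √[(0.35 × 0.65 + 0.371 × 0.629)/8,134.2] = 0.007527
- Power = Φ[(0.021 − 1.96 × 0.007529)/0.007527] = Φ(0.83) = 79.7%

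The same formula asks for 8,206 per arm for 80%, which is 0.9% more than are available. The stated power therefore reproduces.

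**Other contrasts, unadjusted.**

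- 1a and 1b (one arm against three): pooled rate (0.35 + 3 × 0.371)/4 = 0.36575, SE₀ = 0.006166, SE₁ = 0.006126. Power = Φ[(0.021 − 1.96 × 0.006166)/0.006126] = 92.7%.
- A Tukey pair among three arms (critical z 2.344, same rates assumed): Φ[(0.021 − 2.344 × 0.007529)/0.007527] = 67.2%.

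**With adjustment.** The SE is multiplied by √(1 − R²), equivalent to an effective n of 8,134.2/(1 − R²).

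| Assumed R² | 0 | 0.5% | 2% | 5% |
|---|---|---|---|---|
| Reduction in SE | – | 0.25% | 1.0% | 2.5% |
| Equivalent extra patients per arm | – | 41 | 166 | 428 |
| Power, single pair (Analysis 2) | 79.7% | 79.9% | 80.5% | 81.6% |
| Power, 1a and 1b | 92.7% | 92.8% | 93.2% | 93.9% |
| Power, Tukey pair (Analysis 3) | 67.2% | 67.5% | 68.2% | 69.8% |
| Detectable difference at 80%, single pair (points) | 2.11 | 2.10 | 2.09 | 2.06 |

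**Reaching 80.0%.** Before exclusions the single pair needs R² = 1 − 8,134.2/8,206, about 0.9%. Exclusions raise this. If 5% were removed (an assumption; the rate is not given), unadjusted power would be 77.6%. Since 0.95 × 8,134.2 = 7,727.5, reaching 80% would then need R² = 1 − 7,727.5/8,206, about 5.8%. An R² equal to the exclusion fraction brings power back to 79.7%, because the two factors cancel in n(1 − e)/(1 − R²).

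**Simulation check.** Age-by-gender cells, single pair, 1,500 runs, R² of 0.8% and 2.3%. Adjusted and unadjusted mean differences agreed within 0.0001. The empirical SE fell from 0.00765 to 0.00761 and from 0.00768 to 0.00759.

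**Side effects.**

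- The logistic check behaves differently under adjustment. The marginal odds ratio is (0.371/0.629)/(0.35/0.65) = 1.0954. With a normally distributed covariate score explaining 2% or 5%, the conditional odds ratio is 1.0975 or 1.1007, so the target moves slightly.
- In 1a the ordinary OLS standard error is about 0.6% too large (ratio 1.0064), which is conservative. Robust standard errors are therefore optional.

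**The case against.** The strongest reply is that nothing is wrong. Unadjusted OLS is a legitimate and transparent choice in a trial of 40,671 patients, and covariates are a matter of preference. That is correct, and it is why the point is only an optional improvement.

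Second, the documents may support only the low end of the assumed range. They report a gender difference that reverses with age, with no size and no main effect of age. They do not say that risk level predicts vaccination, and its range is restricted to the top 11–20%. As an illustration, take a crossing gender gap of 5 points in two equal age halves. It gives R² = (0.05²/4)/0.2275 = 0.27% and single-pair power of 79.8%; a 10-point gap gives 1.1% and 80.1%. This stands: an R² of 2% to 5% would need an age or risk gradient that the documents do not state.

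Third, changing three confirmatory models after the messages were sent is a second departure from the preregistration. The time was also short: six weeks from 9/13/22 and 9/14/22 end on 10/25/22 and 10/26/22, and the document is dated 10/25/2022. This is a real cost, but outcome data had not been obtained, so pre-specification was still credible.

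Fourth, the open clause on further checks and the exploratory models with age, gender and risk level might seem to cover the point. They do not, because neither fixes an adjusted version of the confirmatory contrasts in advance.

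**Conclusion.** The point holds as a low-priority, optional improvement. Arm is the only predictor named in Analyses 1a, 1b, 2 and 3, and baseline variables that the trial will use anyway are left out. At an assumed R² of 0.5% to 5%, adjustment adds about 0.2 to 2.0 points of power to Analysis 2, 0.3 to 2.6 points to a Tukey pair, and 0.1 to 1.2 points to 1a and 1b. The primary question therefore gains little. The sizes rest on equal allocation, the protocol's planning rates, no exclusions and an R² that the documents do not give. The planned analyses are valid without the change.

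**What to change.** Before outcome data are obtained, name age, gender, age by gender and risk level as covariates in the OLS models for 1a, 1b, 2 and 3.

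- **Age coding.** Enter age as continuous or in a complete set of bins. The exploratory bins cannot be reused, because they omit ages 25–34 and 55–64.
- **Missing values.** Provide a category for any missing baseline value.
- **Portal and SMS eligibility.** Include it only if it was fixed at randomisation and recorded identically in all five arms. The Message Modalities section covers only four: "Patients randomized to arms 2-5 were sent messages in up to 3 modalities, depending on eligibility". Arm 1 is the comparator in 1b and Analysis 2.
- **Sensitivity analysis.** Keep the unadjusted OLS models as a named sensitivity analysis.
- **Logistic check.** Leave it unadjusted, or report it as a marginal risk difference.

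The cost is a few dated lines in the SAP and some age coding, with no new data. The change should be disclosed as the second to the preregistered plan, after the change in the primary outcome time frame.

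### The six other pre-specified outcomes run from an arm-specific start to a fixed end date, so arms 3 and 4 have one day less follow-up than arms 2 and 5 (a minor bias that is easily removed)

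*Combined protocol and SAP*

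**What the plan says.** Under Change in Primary Outcome Time Frame, the plan explains that letters for two arms went out a day late. It therefore moves the primary outcome to "within 6 weeks of the patient's study start date, so all patients can be monitored for the same length of time".

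The same section ties the start date to the letter date of the arm. Active Control (arm 2) and the algorithm arm (arm 5) start on 9/13/22. The other two risk arms (3 and 4) start a day later: "9/14/22: High Risk Only and High Risk Based on Medical Records". Passive Control (arm 1) patients are randomized to one of the two dates.

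Under Other Pre-specified Outcomes, all six outcomes start on that date and stop on a fixed calendar date:
- Outcomes 1, 2 and 6 (two flu diagnoses, COVID-19 vaccination) run "from the patient's study start date through April 30, 2023".
- Outcomes 3, 4 and 5 (flu complications, ER visits, hospitalizations) run to the end of July. ER visits are defined as "Number of ER visits from the patient's study start date through July 31, 2023", and hospitalizations in the same way.

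No rate, offset or equal-length rule is given for these outcomes. The section restricts their analysis to comparisons in which flu vaccination differs significantly.

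Analysis Exclusion Criteria removes patients who had a flu shot, or died, before their own start date. That cut-off also differs by arm.

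**The concern.** A start that varies by arm combined with a common end makes the length of follow-up depend on the assigned arm. The plan saw this problem for the primary outcome and removed it, but did not carry the remedy over to the other six.

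The direction is known, because arms 3 and 4 can only lose a day of events. With no true effect, Analysis 1a (arms 3–5 v arm 2) would show slightly fewer ER visits and hospitalizations under the risk messages, which looks like benefit. It would also show slightly fewer COVID-19 vaccinations, which looks like harm. A larger sample does not remove the bias. Because the plan attributes any arm difference in these outcomes almost entirely to flu vaccination, a difference due to follow-up length would be credited to the wrong cause.

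**Working it through.** **Inputs from the document.** Sample: "The sample includes 40,671 patients". Arms: "This study is a randomized controlled trial with 5 study arms". Start and end dates are as given above.

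**Assumptions, because the document does not give them.** Equal allocation, so 40,671/5 = 8,134.2 per arm; a 50:50 split of start dates in arm 1; a constant event rate; event means over a range.

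**The plan's own figure.** Power Analysis states "80% power to detect an increase in flu vaccination rates from 35% to 37.1% with two-tailed alpha = .05". With 8,134.2 per arm, SE = √[(0.35×0.65 + 0.371×0.629)/8,134.2] = 0.00753, and 0.021/0.00753 − 1.96 = 0.83, so power is 79.7%. The figure reproduces under equal allocation. The present point does not depend on it.

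**Days of follow-up, counting both end days.**
- To April 30, 2023: 18+31+30+31+31+28+31+30 = 230 from 9/13, and 229 from 9/14.
- To July 31, 2023: 230+31+30+31 = 322 from 9/13, and 321 from 9/14.
- Primary outcome: six weeks in every arm, difference 0.

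**Average shortfall by planned comparison.**

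| Comparison | Shortfall (days) | % of 230 | % of 322 |
|---|---|---|---|
| 1a: arms 3–5 v arm 2 | 2/3 = 0.67 | 0.29 | 0.21 |
| 1b: arms 3–5 v arm 1 | 2/3 − 1/2 = 0.17 | 0.07 | 0.05 |
| 2: arm 1 v arm 2 | 0.5 | 0.22 | 0.16 |
| 3: arm 3 or 4 v arm 5 | 1 | 0.43 | 0.31 |
| 3: arm 3 v arm 4 | 0 | 0 | 0 |

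**Size of the 1a bias with no true effect.** Bias = event mean × shortfall/window. SE = SD × √(1/8,134.2 + 1/24,402.6) = SD × 0.0128.
- Counts with mean 0.5 and variance equal to the mean: bias 0.5×0.667/322 = 0.00104, SE 0.707×0.0128 = 0.00905, ratio 0.114.
- Counts with mean 0.3 to 1.0 and variance 1 to 3 times the mean: 0.05 to 0.16 SE. The highest case tried (mean 2.0, variance equal to the mean) gives 0.23 SE and a rejection rate of 5.6% instead of 5%.
- COVID-19 vaccination at 20%: bias 0.20×0.667/230 = 0.058 points, 0.113 SE, rejection rate 5.15%. At 40%: 0.116 points, 0.185 SE, 5.4%.

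**Other comparisons, same method** (count means 0.2 to 2.0, binary rates 2 to 40%). 1b stays below 0.06 SE, and Analysis 2 reaches at most 0.14 SE. The one-day contrasts in Analysis 3 reach at most 0.28 SE, a rejection rate of 5.9% for an unadjusted pairwise test.

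**Why moving the window alone is not enough.** A flu shot on 9/13 removes a patient from arms 3 and 4 but not from arms 2 and 5. As an illustration only, assume 40% COVID-19 uptake and three times the average daily uptake on 9/13, so q = 3×0.40/230 = 0.522 points. Assume also that every such dose came with a flu shot and that no other flu shots were given that day.
- Arms 3 and 4, after exclusion: (0.40 − q)/(1 − q) = 39.69%.
- Plan as written: arms 2 and 5 stay at 40%, so the 1a bias is (2/3)×(39.69 − 40.00) = −0.21 points.
- Window moved to 9/14, exclusions unchanged: arms 2 and 5 become 40 − 0.522 = 39.48%, so the bias is (2/3)×(39.69 − 39.48) = +0.14 points.

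The sign reverses and the bias remains. With both the window and the exclusions set at 9/14 in every arm, the difference is zero.

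**The case against.** The strongest reply is that one day in 230 to 322 has no practical consequence. The bias would not be visible in the data, the primary outcome is untouched, and these outcomes are examined only after a significant flu vaccination difference. Analysis 3 is exploratory as well. All of that stands, and it keeps the point minor.

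It can also be said that the equal-length rationale, "so all patients can be monitored for the same length of time", is given for the primary outcome only, and that a season-end cut-off is a legitimate separate choice. That is right. A reader might infer that the plan contradicts itself, but it does not; a principle was applied to one outcome and not extended to the others.

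Two stronger readings are tempting and not supported:
- **A type I error of 6–9% for COVID-19 vaccination.** This needs three times the average uptake on September 13. Nothing in the document supports that, and the calculation ignores the flu-shot exclusion.
- **A bias that is large against the effect sought.** If the 2.1-point vaccination gain were the only mechanism, a 0.21% drop would require vaccination to prevent about 10% of all ER visits (0.207/2.1 = 9.9%). But the plan sets no target effect for ER visits, and the comparison says more about how little that outcome can show than about the lost day.

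The constant-rate figures may also overstate the bias for the flu outcomes (1–3), if few flu events occur on September 13.

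**Conclusion.** The point holds as a minor inconsistency. Arms 3 and 4 have one day less follow-up than arms 2 and 5 for all six outcomes, and the raw counts are not adjusted for it. The day counts follow directly from the document. The size in standard errors rests on assumed event means, equal allocation and a constant event rate; for 1a it is about 0.2 SE or less across plausible values, and much smaller for 1b. The direction is known. The document does not support reading this as a threat to the primary result or to the trial's conclusions. It deserves correction because the bias is systematic, the plan has already dealt with the same one-day slip for its primary outcome, and Project Status says that no outcome data had yet been obtained.

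**What to change.** For Other Pre-specified Outcomes 1–6, start the count on September 14, 2022 in every arm and keep the fixed end dates. For these analyses, also apply the prior-flu-shot and prior-death exclusions as of September 14, 2022 in every arm. Window (229 and 321 days), calendar days and analysis set then match across arms, and the random start date in arm 1 is not needed for these outcomes. The primary analysis stays as written.

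Cost: a change of wording in six definitions plus one sentence on the analysis set. One day of events is lost in arms 2 and 5 and about half of arm 1 (1/230, at most about 0.4% of follow-up), along with the few patients in those arms vaccinated or deceased on September 13. For arms 2 and 5 the count no longer begins on the letter date, and the analysis set differs slightly from the primary one.

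A person-time offset would address only the two count outcomes. Equal-length windows from each patient's own start would equalize length but not calendar days.
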